Spasmodic Dysphonia Pain Study

NCT04648891

7/5/2020

General Study Information

Principal Investigator: [name]

Study Title: Spasmodic Dysphonia Pain Study

Protocol version number and date: Version 1. 07/05/20

Research Question and Aims

Hypothesis: The use of local anesthetic or vibrating instrument will decrease overall pain experienced by a patient with spasmodic dysphonia undergoing Botox injections.

Aims, purpose, or objectives: To identify adjuvant methods to improve patient comfort during in-office laryngology procedures. Results demonstrated here should be transferrable to other transcutaneous in office procedures in laryngology.

Background (Include relevant experience, gaps in current knowledge, preliminary data, etc.):

BACKGROUND AND SIGNIFICANCE

Spasmodic Dysphonia (SD)

Spasmodic dysphonia (SD) is a task-specific focal laryngeal dystonia characterized by irregular and uncontrolled voice breaks that interrupt normal speech flow.¹ The condition was first described by Critchley in 1939 and was for some time considered a psychiatric disorder.² The estimated prevalence in western society is between 1 in 50,000 and 1 in 100,000.^{3,4} There are likely multiple neurological processes involved in the pathophysiology of SD: reduced cortical inhibition, sensory-processing and reflex disturbances, and neuroanatomical findings at several different levels. Thus, SD should be considered an integrative system disorder, rather than a disorder with a single pathological focus.¹ Its etiology is multifactorial, including neurological, genetic, and environmental factors. Epidemiological risk factors have been suggested from several large cohort studies. The most commonly identified characteristics are females in their middle decades of life, a family history of neurological diseases including dystonia, recent life stressors, upper respiratory tract infections, and a history of childhood measles or mumps.¹ The eventual development of SD may be viewed as a multiple-hit mechanism, with endogenous predispositions and environmental triggers resulting in the development of its phenotype. Adductor spasmodic dysphonia (AdSD), characterized by a harsh, strain-strangled voice with breaks on vowels in speech, is the most common variant of the condition.⁵ Vocal tremor co-occurs in 30% to 60% of AdSD patients.^{1,5}

A three-tiered approach, involving clinical history, followed by speech assessment and in-office laryngoscopy is the most widely accepted method for making the diagnosis of SD.⁵ Diagnosis is often made years after symptom onset and following assessment by numerous physicians.⁶ In clinical practice, a history of speech therapy failing to ameliorate symptoms and positive treatment response to botulinum neurotoxin is a reliable adjunct to diagnosis. Botox (onabotulinumtoxinA) is the most frequently used and studied formulation of botulinum neurotoxin.

Based on the significant symptom response of blepharospasm to intermittent injections of Botox, Blitzer et al. performed the first laryngeal injection of Botox for SD in 1984.^{7,8} Botulinum neurotoxin is internalized at the nerve terminal and works by cleaving proteins in the SNARE (soluble n-ethylmaleimide-sensitive factor [NSF] attachment protein receptor) complex, which facilitate the binding of vesicles containing acetylcholine to the nerve terminal.^{9,10} Botulinum neurotoxin cleaves SNAP-25 inhibiting presynaptic acetylcholine release and muscle activity.⁹ The precise mechanism by which botulinum neurotoxin improves SD symptomatology is unknown. Its effect is not fully explained by chemodenervation of the thyroarytenoid muscle since other adductor muscles are relatively unaffected and some patients experience improvement in concurrent extralaryngeal dystonias.⁹ It may therefore result in disease modulation at a central level.¹¹

Despite its use in the larynx being considered "off-label" by the U.S. Food and Drug Administration (FDA), botulinum neurotoxin has remained the first-line treatment for spasmodic dysphonia.¹² botulinum neurotoxin is the recommended primary management strategy in the American Academy of Otolaryngology-Head and Neck Surgery's Clinical Practice Guideline for dysphonia.¹³ Alternative treatment options for SD include surgical treatments, which include thyroarytenoid myotomy/myectomy, thyroplasty, selective laryngeal adductor denervation-reinnervation, laryngeal nerve crush, and recurrent laryngeal nerve resection.¹⁴ There are no published randomized controlled trials comparing the effect of Botox injections and surgical treatment.¹⁴ A systematic review published in 2017 reported that preference for one treatment could not be demonstrated.¹⁴ The effect of bilateral Botox injections was evaluated and the authors found an improvement in the objective outcome, subjective outcome, and quality of life. The mean duration of effect ranged between 14 and 18 weeks. There is currently no cure for the condition. Thalamic deep brain stimulation may become a future treatment option to interfere with the central pathophysiology of SD.¹⁵

Laryngeal Injections

In-office procedures are increasingly common in laryngology.¹⁶ Their success is dependent on adequate analgesia, and while these procedures are generally considered to be well-tolerated, few studies address pain or patient experience. A systematic review published in 2019 analyzed the literature for studies reporting qualitative or quantitative data for periprocedural pain assessment in adult patients undergoing in-office otolaryngology procedures.¹⁶ A total of 86 studies met inclusion criterial, of which 31 related to laryngology. Of the 86 studies, only 13 were prospective studies comparing interventions and none of these studies addressed analgesia in laryngeal injections.¹⁶ This study will be the first to compare the impact of anesthetic techniques in laryngeal injections.

Vocal fold injections (VFI) are commonly performed in-office procedures in laryngology that can be used as a treatment modality in vocal fold paralysis and in a number of other laryngeal pathologies, in addition to enabling the injection of botulinum neurotoxin in the treatment of SD. These can be performed transcutaneously (with multiple techniques), transnasally, or transorally. The transcricothyroid approach (a needle is passed through the skin, soft tissue, and cricothyroid membrane) is the most studied technique overall. Specific to the treatment of SD, a transcricothyroid approach is favored by 90% of laryngologists treating SD with botulinum neurotoxin.¹²

The patient experience and pain associated with laryngeal injections have been previously studied.^{17,18,19} Young et al. reported the patient tolerance of 154 in-office laryngeal procedures including 108 VFIs, of which 8 were Botox injections.¹⁷ Transcutaneous VFI was performed following injection of subcutaneous local anesthetic. The rate of completion of the first-choice VFI approach was 93%. Average patient-reported pain on the VAS was approximately 40. There was no statistically significant difference in pain between percutaneous and peroral VFI approaches (VAS 43.1 versus 38.4). Discomfort score differed significantly between those patients who had a VFI successfully completed with the first-choice VFI technique versus those who required more than one VFI approach (36.03 versus 61.29).¹⁷ Birkent et al. enrolled 26 patients receiving VFI with a transcricothyroid approach under local anesthesia with a mean reported VAS of 44.¹⁸ Crawley et al. enrolled 45 patients to study the perception and duration of pain after VFI.¹⁹ Injection was performed with a transcricothyroid approach following local and topical anesthesia. Almost 80% of patients reported increased pain from baseline to during the procedure and from baseline to after the procedure. The majority of patients reported that their pain persisted or worsened during the first post-procedure day. Almost half of patients took additional pain medication. A third of patients were still experiencing some discomfort on the third postprocedure day. They found that the magnitude of the increase in pain during the procedure was significantly associated with the presence of pain on the third post-procedure day. This data supports the hypothesis that nociceptive sensitization is responsible for lingering pain. In this study, patients reported a significant increase in sickening and punishing sensations as well as exhaustion and fear during the procedure.¹⁹ None of these studies controlled or compared anesthetic techniques. In each of the aforementioned studies, subcutaneous local anesthetic was delivered prior to transcutaneous injections. However, one-third of laryngologists report not using local anesthesia when treating SD with Botox.¹² Nor were alternative anesthetic techniques utilized.

Vibration Anesthesia

Vibratory stimulation is defined as the performance of continuous, quick, slight shaking movements on the skin using devices or fingers.²⁰ The application of a vibratory stimulus has been shown to improve patient discomfort associated with various needle-related procedures including botulinum neurotoxin injections for cosmetic indications.²¹ The application of intense stimuli to the skin as a means of pain relief is not a novel concept.²² Countless generations of bruised knees have been taken to mother so that she could "rub it to make it better". Ancient Greeks used vigorous massage to deal with sporting injuries, and by the early renaissance, de Mandeville was able to include percussion as a recognized treatment for pain. Percussion analgesia for amputation stump pain was recognized in the aftermath of the American Civil War, but this approach was not reported until the mid-1940s.²²

In the 1960s a mechanism for the anesthetic capability of vibration was proposed. Melzack and Wall's "gate control" theory of pain postulates that the intensity of pain can be reduced by concurrent non-noxious stimulation, such as vibration.²³ Their hypothesis states that the transmission of the sense of vibration from mechanoreceptors located in the skin via A- β nerve fibers results in the shutting down of a "gate" through which pain signals are transmitted to the brain through A- δ and C fibers.²³ Despite this physiologic concept being well-recognized, in addition to much empirical evidence existing to support its validity, prospective controlled trials assessing its utility during awake procedures have only recently been produced.

A number of studies exist in the facial plastic surgery literature analyzing the analgesic properties of vibratory stimulation while performing cosmetic injections.^{21,24-26} Sharma et al. applied a vibratory stimulus during the cosmetic facial injection of Botox.²¹ There was a statistically significant reduction in patient's pain scores (1.3 vs 2.4 on a five-point Likert-type scale). Of the 50 patients, 82% noted that the vibration side of the face had lower pain than the side of their face injected without vibration. Further, 86% these patients preferred to utilize vibratory analgesia for subsequent injections.²¹ Mally et al. applied a vibratory stimulus during injection of the nasolabial folds with dermal filler.²⁴ They found improved patient tolerance with vibratory stimulation. While 88% of patients found the injections moderate to severely painful without vibration, only 14% with vibration experienced moderate to severe pain.²⁴ This finding was replicated by Guney et al. in a randomized split-lip study assessing vibration anesthesia during lip augmentation with cosmetic filler.²⁵ The overall pain score on the vibration-assisted side was significantly reduced (3.8 vs 5.6 on a ten-point Likert-type scale). Of the 25 patients enrolled in this study, 23 stated that they would want to have vibration anesthesia for future injections. The 2 patients who declined vibration stimuli for the future stated that they felt an increase of pain and anxiety with the addition of vibration. Both of these patients underwent lip augmentation for the first time. All patients that had undergone previous lip augmentation treatments expressed a desire for vibration anesthesia in the future.²⁵ Chorney et al. published a prospective, randomized, self-control trial of cosmetic botulinum toxin injections comparing vibration anesthesia to topical ice analgesia to no additional analgesia.²⁶ There were 30 injections given with vibration analgesia, with a mean VAS of 26.5. There were 28 injections given with ice that resulted in a mean VAS of 24.4. Among the 30 injections given without any analgesia, patients had mean VAS of 29.4. There was no statistically significant difference between these groups. Of note this study design resulted in a lack of power given only a maximum of 30 injections were present in each arm.

There is additional support for the analgesic properties of vibratory stimulation outside of the facial plastic surgery literature. A systematic review evaluated evidence of the effectiveness of vibratory stimulation to reduce needle-related procedural pain in children.²⁰ The meta-analysis of this systematic review showed

that vibratory stimulation was significantly effective according to both self-rated and observer-rated pain measurements regardless of age group, type of procedure, or type of vibration device.²⁰ Within the dermatology literature further support can be found. Park et al. studied VAS scores when vibration anesthesia was used during keloid triamcinolone injections. Intralesional injection therapy without vibration yielded mean VAS scores of 59 compared to 33 when vibration was used (P < .05).²⁷ Fix et al. studied vibration anesthesia during the injection of lidocaine in an open label, randomized, controlled, split-body trial. The median VAS pain score was 26 for injections without vibration versus 7.5 with vibration (P<0.01).²⁸

However, no study to date has analyzed the use of vibration analgesia during VFI.

Study Design and Methods

Methods: Describe in lay terms, completely detailing the research activities that will be conducted by Mayo Clinic staff under this protocol.

Each patient will undergo each of the three treatment modalities. The order in which they receive these will be randomized.

Treatment Group A (control): No anesthesia

Treatment Group B: 0.5cc subcutaneous 2% lidocaine in 1:100,000 epinephrine (done approximately 2 minutes before Botox injection)

Treatment Group C: Vibrating instrument held adjacent to cricothyroid space as Botox injection is performed

The nurse assisting the procedure will also time the Botox portion of the procedure to enable analysis of whether pain is associated with longer procedure time.

Patient participation is expected to last approximately 6-12 months. The study specific questionnaire #1 will be given at only their first visit. Study specific questionnaire #2 will be given immediately after each Botox injection.

Subject Information

Target accrual is the proposed total number of subjects to be included in this study at Mayo Clinic. A "Subject" may include medical records, images, or specimens generated at Mayo Clinic and/or received from external sources.

Target accrual: 50

Subject population (children, adults, groups): Adults with spasmodic dysphonia

Inclusion Criteria:

-spasmodic dysphonia with or without tremor -receiving botox as treatment via a transcricothyroid approach

Exclusion Criteria:

-allergy to lidocaine

Biospecimens

Collection of blood samples. When multiple groups are involved copy and paste the appropriate section below for example repeat section b when drawing blood from children and adults with cancer.

a. From healthy, non-pregnant, adult subjects who weigh at least 110 pounds. For a minimal risk application, the amount of blood drawn from these subjects may not exceed 550ml in an 8 week period and collection may not occur more frequently than 2 times per week.

Volume per blood draw: ____ml

Frequency of blood draw (e.g. single draw, time(s) per week, per year, etc.)

b. From other adults and children considering age, weight, and health of subject. For a minimal risk application, the amount of blood drawn from these subjects may not exceed the lesser of 50 ml or 3 ml per kg in an 8 week period, and collection may not occur more frequently than 2 times per week. Volume per blood draw: ml

Frequency of blood draw (e.g. single draw, time(s) per week, per year, etc.)

Prospective collection of biological specimens other than blood:

Review of medical records, images, specimens

Check all that apply (data includes medical records, images, specimens).

Only data that exists before the IRB submission date will be collected.

Date Range for Specimens and/or Review of Medical Records:

Examples: 01/01/1999 through 12/31/2015, or all records through mm/dd/yyyy.

Note: The Date Range must include the period for collection of baseline data, as well as follow-up data, if applicable.

X The study involves data that exist at the time of IRB submission **and** data that will be generated after IRB submission. Include this activity in the Methods section. Examples

- The study plans to conduct a retrospective chart review and ask subjects to complete a questionnaire.
- The study plans to include subjects previously diagnosed with a specific disease and add newly diagnosed subjects in the future.

The study will use data that have been collected under another IRB protocol. Include in the Methods section and enter the IRB number from which the research material will be obtained. *When appropriate, note when subjects have provided consent for future use of their data and/or specimens as described in this protocol.*

Enter one IRB number per line, add more lines as needed

🗌 Data	Specimens Data & Specimens	
🗌 Data	Specimens Data & Specimens	
🗌 Data	Specimens Data & Specimens	

Data Analysis

Power analyses may not be appropriate if this is a feasibility or pilot study, but end-point analysis plans are always appropriate even if only exploratory. Provide all information requested below, or provide justification if not including all of the information.

Power Statement:

Sample size estimation is estimated based on the repeated methodology; that is, the VAS score will be measured at three time points (initial visit, 3 months and 6 months) for each patient. The comparisons between treatment arms (treatment B and C) and control arm (A) are of interest. To preserve the family wise type I error rate, 0.05, Bonferroni approach is used to adjust the pairwise type I error (0.05/2 = 0.025). We further assume the standard deviation across subjects at the same time point is 3.00, and there is a weak correlation between the VAS (<= 0.3) within each patient. To achieve 80% to detect statistically significant differences in the mean VAS between A and B, and between A and C, the required sample size based on different value of correlation are listed below:

VAS			Required sample size		
Α	В	С	Correlation $= 0.3$	Correlation $= 0.1$	Correlation =
					0.05
4	1	1	18	21	22

	2	2	32	40	42
	3	3	114	145	153
5	2	2	18	31	22
	3	3	33	40	42
	4	4	114	145	153
6	2	2	13	14	14
	3	3	18	21	22
	4	4	32	40	42
	5	5	114	145	153

Note: The weaker the correlation and the smaller the mean difference in VAS the larger the sample size. Randomization schedule will be generated by the study statistician. Randomization will determine the order they get these treatments and can follow any permutation.

Data Analysis Plan:

Data Handling

The study data will be entered and saved in REDCap. The REDCap database will be created by the study personnel. Only the PI and study personnel will have access to the database. Data analysis

Data will be summarized by mean (standard deviation) or median (interquartile range) for continuous variables, and frequency count (percentage) for categorical variable. The number of patients without the VAS score at 3- and 6-months after the initial visit will be reported. Generalized estimating equation will be used to compare the mean VAS score between groups, and the point estimate of the mean difference and 95% confidence interval will be reported.

Endpoints

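### Multiplicity control appears only in the Power Statement; naming Holm's procedure in the Data Analysis Plan keeps the 0.05 family-wise error and adds 2 to 4 points of power per comparison at a 2-point difference

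*Combined protocol and SAP*

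**What the plan says.** Under Data Analysis, the Power Statement defines the family: "The comparisons between treatment arms (treatment B and C) and control arm (A) are of interest". It then sets the level: "To preserve the family wise type I error rate, 0.05, Bonferroni approach is used to adjust the pairwise type I error (0.05/2 = 0.025"). The sample-size table is built to detect differences "between A and B, and between A and C" with 80% power, SD 3.00 and within-patient correlation of 0.3, 0.1 or 0.05. Every row gives B and C the same effect.

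The Data Analysis Plan, the next subsection, names GEE for the comparison of mean VAS and says that "the point estimate of the mean difference and 95% confidence interval will be reported". It states no significance level, no multiplicity procedure and no list of the pairs to be tested. Subject Information gives "Target accrual: 50". The hypothesis under Research Question and Aims reads "The use of local anesthetic or vibrating instrument will decrease overall pain".

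**The concern.** Two things are left open.

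- **The test level at analysis.** The sample size rests on 0.025 per comparison, but a 95% interval corresponds to 0.05 per comparison. An analyst who follows the Data Analysis Plan alone could judge A–B and A–C each by whether its 95% interval excludes zero, and the family-wise protection that the Power Statement sets out to preserve would be lost.
- **The choice of procedure.** Once a procedure has to be named, plain Bonferroni gives away power when both interventions work, which is the case in every row of the sample-size table. Holm recovers part of that power at no cost in family-wise error.

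What is at stake is the chance of confirming the second intervention, not the validity of the trial.

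**Working it through.** **Inputs.** From the Power Statement: SD 3.00; correlation ρ = 0.05, 0.1, 0.3; family-wise level 0.05 over two comparisons; a 2-point difference for both B and C (table rows 4/2/2, 5/3/3 and 6/4/4). From Subject Information: n = 50. Assumed, because the plan does not say: two-sided tests, 50 complete patients, and paired t-tests standing in for the GEE contrasts.

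**Step 1: reproduce the plan's figure.** The SD of a within-patient difference is 3·√(2(1−ρ)). For 80% power at two-sided 0.025 and a 2-point difference:

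| | ρ = 0.3 | ρ = 0.1 | ρ = 0.05 |
|---|---|---|---|
| Plan's table | 32 (33 in row 5/3/3) | 40 | 42 |
| Paired t, n−1 df, at 0.025 | 33 | 42 | 44 |
| t with 2(n−1) df, at 0.025 | 32 | 40 | 42 |
| Paired t, n−1 df, at 0.05 | 27 | 34 | 36 |

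The 2-point rows reproduce at 0.025 and not at 0.05, so the sample size does rest on Bonferroni.

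**Step 2: Bonferroni power at n = 50.** The noncentrality is 2·√50 / SD of the difference, and the two-sided 0.025 critical value on 49 df is 2.312.

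- ρ = 0.05: SD 4.135, noncentrality 3.420, power 86.2%.
- ρ = 0.1: SD 4.025, noncentrality 3.514, power 88.1%.
- ρ = 0.3: SD 3.550, noncentrality 3.984, power 94.9%.

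**Step 3: Holm.** Holm tests the smaller p-value at 0.025 and, if it is significant, the other at 0.05. For one comparison the gain is P(own p between 0.025 and 0.05, and the other p below 0.025). With equal effects, the gain in showing both is twice that. Simulation from three exchangeable normal measures per patient (100,000 replicates per scenario, confirmed by a separate run of 400,000):

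| Scenario, n = 50 | Per comparison, Bonferroni → Holm | Both significant, Bonferroni → Holm |
|---|---|---|
| 2 points each, ρ 0.05 | 86.2% → 90.2% | 77.4% → 85.4% |
| 2 points each, ρ 0.1 | 88.1% → 91.7% | 80.3% → 87.6% |
| 2 points each, ρ 0.3 | 95% → 97% | 91.1% → 95.2% |
| 1.5 points each, ρ 0.1 | 63% → 69% | 46.9% → 58.4% |
| 1 point each, ρ 0.05 to 0.3 | +3.5 to +4.7 points | +7.2 to +9.3 points |
| 3 points each | at most +0.2 points | at most +0.3 points |
| 2 and 1 points, ρ 0.1 | weaker one 29.8% → 40.0% | 29.0% → 39.7% |
| Only B works (2 points), ρ 0.1 | B 88.2% → 88.3% | not applicable |

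The chance of at least one significant result is the same under both methods (94.9% at 2 points, ρ 0.05). This follows from the rule, since Holm's first step is the Bonferroni test.

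**Step 4: error rates.** With no true effect (ρ 0.1), the family-wise error is 4.7% under Bonferroni and under Holm, and 9.1% for two unadjusted tests at 0.05. With only B effective, the false-positive rate for C rises from 2.5% to 4.5%, still within 0.05.

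**Step 5: closer to the planned analysis.** With complete data and uncorrected robust Wald z-tests in place of paired t, the gains at 2 points are +3.5 per comparison and +6.9 for both (ρ 0.05), and +1.6 and +3.1 (ρ 0.3). Null family-wise error is 5.7% under both methods.

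**The case against.** The strongest reply is that the rule is already stated. The family, the family-wise level, the method and the pairwise level all sit under the same Data Analysis heading, and Bonferroni can be read as covering the analysis. On that reading the defect is a missing cross-reference and a mismatched interval level, and one clause carrying Bonferroni forward with 97.5% intervals would cure it. That is fair: Holm is not the only way to close the gap. The 9% also applies only if the 95% intervals are used as the tests, which the plan does not say.

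A second point concerns the intervals. Every extra Holm rejection has p between 0.025 and 0.05, so its 97.5% interval includes zero. At 2 points this occurs in 8.0% of trials at ρ 0.05 and 4.0% at ρ 0.3. This stands, and it is why the adjusted p-value must be named as the decision rule. Bonferroni with 97.5% intervals has no such conflict.

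Third, with uncorrected robust standard errors and only B effective (ρ 0.1), the false-positive rate for C is 3.2% under Bonferroni and about 5.4% under Holm. This is small-sample inflation of the uncorrected robust test. Bonferroni shows it too, at 5.7% under the global null, so Holm does not raise the worst-case error.

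Finally, little is at stake at 2 points, where Bonferroni already exceeds the planned 80%, and the larger gains (1.5 points; 2 and 1 points) use effect patterns that are not in the plan's table. The hypothesis is worded with "or" in the sense of "The use of local anesthetic or vibrating instrument will decrease overall pain"; if one positive result is enough, Holm adds nothing.

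**Conclusion.** The concern holds as an improvement, not as the repair of an invalid method. The Data Analysis Plan names no multiplicity procedure, and its 95% intervals do not match the 0.025 planning level. Holm keeps strong 0.05 family-wise control under any dependence between the two tests. At n = 50 and a 2-point difference for both interventions it adds 2 to 4 points of power per comparison and 4 to 8 points for showing both; with uncorrected robust z-tests the per-comparison gain is 1.6 to 3.5 points.

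These figures assume SD 3, correlation 0.05 to 0.3, two-sided tests, complete data and both interventions effective. No dropout rate is given; with 40 to 45 completers the per-comparison gain is about 2.7 to 5.4 points. The gain is negligible at 3 points or when only one intervention works. It matters only if lidocaine and vibration are each to be judged separately.

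**What to change.** Leave the Power Statement and its sample size on the conservative 0.025 basis. Add to the Data Analysis Plan, before any outcome data are examined:

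> *The two-sided GEE p-values for A–B and A–C will be tested by Holm's procedure: the smaller at 0.025 and, if it is significant, the other at 0.05. The Holm-adjusted p-value is the decision rule. 97.5% confidence intervals will be reported alongside.*

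The cost is one statement, with no change to design or accrual. The downside is that the 97.5% interval for the second comparison can include zero when its Holm test is significant. If the sponsor prefers test and interval always to agree, the acceptable alternative is to state Bonferroni at 0.025 in the Data Analysis Plan with 97.5% intervals and forgo the extra power. Under either choice, the plan should say whether the GEE standard errors carry a small-sample correction, because uncorrected ones give slightly more than 5% family-wise error at n = 50.

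### Sample-size table: one cell (31) contradicts its sibling rows and the table's own note, and, if the tests are two-sided, the 1-point cells give about 77% pairwise power, not 80% (minor)

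*Combined protocol and SAP*

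**What the plan says.** All the sizing is in the Power Statement, under Data Analysis in the combined protocol and SAP. Its basis is described only as "Sample size estimation is estimated based on the repeated methodology". On the hypotheses it says "The comparisons between treatment arms (treatment B and C) and control arm (A) are of interest", and on the error rate "Bonferroni approach is used to adjust the pairwise type I error (0.05/2 = 0.025". It assumes an SD of 3.00 and a within-patient correlation of at most 0.3. It then tabulates sample sizes "To achieve 80% to detect statistically significant differences in the mean VAS between A and B, and between A and C".

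The table, regrouped by the difference between A and each of B and C (correlation 0.3 / 0.1 / 0.05):

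| Difference | Rows (A/B/C) | Printed n |
|---|---|---|
| 1 point | 4/3/3, 5/4/4, 6/5/5 | 114 / 145 / 153 in all three |
| 2 points | 4/2/2, 6/4/4 | 32 / 40 / 42 |
| 2 points | 5/3/3 | **33** / 40 / 42 |
| 3 points | 4/1/1, 6/3/3 | 18 / 21 / 22 |
| 3 points | 5/2/2 | 18 / **31** / 22 |
| 4 points | 6/2/2 | 13 / 14 / 14 |

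The note under the table reads "The weaker the correlation and the smaller the mean difference in VAS the larger the sample size". The analysis section says "Generalized estimating equation will be used to compare the mean VAS score between groups" and that "the point estimate of the mean difference and 95% confidence interval will be reported". Subject Information gives "Target accrual: 50".

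**The concern.** With one SD for all scores, the required n depends on the difference and the correlation, not on the level from which pain starts. Rows with the same difference should therefore be identical, and the 5/2/2 row is not. Its middle entry also breaks the note, because 31 at correlation 0.1 exceeds 22 at the weaker correlation of 0.05.

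The second matter is what the 80% refers to. The text names two pairwise comparisons at a Bonferroni level but no test and no sidedness, and the printed numbers do not come out of the usual two-sided paired calculation. This table is the plan's only sample-size justification, so a reader should be able to tell which hypothesis carries the stated power.

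**Working it through.** **Inputs.** SD 3.00, correlation ρ = 0.3, 0.1 or 0.05, alpha 0.025 per comparison and power 80%, all from the Power Statement. The Methods section has every patient receive all three modalities, so A vs B and A vs C are paired. Sidedness is not given; both are tried.

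**1. Internal consistency.** This needs no outside assumption. The three 3-point rows give 21, 31 and 21 at ρ = 0.1. The note requires the value at 0.1 to be no larger than the 22 at 0.05; 21 satisfies it and 31 does not. At n = 31 the power would be 95.8% by two-sided paired t. The methods tried (paired t and normal, one- and two-sided; overall tests of the three means; A against the average of B and C) give 15 to 22 for this cell.

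**2. Can the printed figures be reproduced?** The closest match found is an overall test of the three means on 2 df at 0.025: F with 2 and n−2 df, noncentrality m × (2/3)d² / [9(1−ρ)]. With m = n−1, for d = 1, ρ = 0.3, n = 114: 113 × 0.667 / 6.3 = 11.96, giving 80.3% power. Required n:

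| Difference | m = n−1 | m = n |
|---|---|---|
| 1 | 114 / 145 / 153 | 113 / 144 / 152 |
| 2 | 32 / 40 / 42 | 31 / 39 / 41 |
| 3 | 17 / 21 / 22 | 16 / 20 / 21 |
| 4 | 12 / 14 / 14 | 11 / 13 / 14 |

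With m = n−1, 24 of the 30 printed cells match exactly and 29 are within one patient. With m = n, only one cell matches exactly, though 29 are within two. Only the 31 is unexplained under either.

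**3. The comparisons the text names.** SD of the paired difference = 3√[2(1−ρ)] = 3.550 / 4.025 / 4.135; its square is 12.6 / 16.2 / 17.1.

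Normal approximation, two-sided 0.025: n = (2.241 + 0.842)² × variance / d². For d = 1 this is 9.505 × 12.6 = 119.8, × 16.2 = 154.0 and × 17.1 = 162.5, so 120 / 154 / 163. Power at the printed n = 114, ρ = 0.3: √114 / 3.550 − 2.241 = 0.767, which is 77.8%.

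The paired t version uses noncentrality d√n / SD of the difference with n−1 df.

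| Difference | Printed n | Needed, paired t | Needed, normal | Power at printed n, paired t (%) | Power at printed n, normal (%) |
|---|---|---|---|---|---|
| 1 | 114 / 145 / 153 | 123 / 157 / 166 | 120 / 154 / 163 | 76.8 / 76.6 / 76.6 | 77.8 / 77.3 / 77.3 |
| 2 | 32 / 40 / 42 | 33 / 42 / 44 | 30 / 39 / 41 | 79.3 / 78.8 / 78.7 | 82.8 / 81.6 / 81.4 |
| 3 | 18 / 21 / 22 | 16 / 20 / 21 | 14 / 18 / 19 | 85.8 / 83.0 / 83.0 | 91.1 / 88.0 / 87.7 |
| 4 | 13 / 14 / 14 | 11 / 13 / 13 | 8 / 10 / 11 | 91.6 / 86.6 / 84.6 | 96.6 / 93.0 / 91.6 |

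The single cell of 33 gives 80.7% by paired t. The 1-point shortfall is 9 / 12 / 13 patients by paired t and 6 / 9 / 10 by the normal approximation.

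**4. One-sided at 0.025.** By paired t the 1-point rows would need only 101 / 130 / 137, and the printed n would give 84.4 to 84.7%. One-sided testing does not explain the table either.

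**5. At the target accrual.** With 50 completers, two-sided paired-t power is 94.9 / 88.1 / 86.2% for 2 points and 38.2 / 29.8 / 28.3% for 1 point.

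**The case against.** *The 31 may not be in the source.* The table reached this review through text extraction that visibly broke its layout, and a single misread digit would turn 21 into 31 or 32 into 33. This stands. A reader might infer that the sponsor's own document is wrong; the text available shows only that the extracted figure cannot be right.

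*The 77% rests on an unstated choice.* The plan gives no sidedness, and its hypothesis is directional: pain is expected to fall. One-sided power would be about 84%. This also stands, so the figure has to be conditional. The planned 95% interval points to two-sided inference, but that is not a statement of the test. Nor has the planned generalized estimating equation been simulated. With complete data and treatment effects only, its contrast is the mean paired difference, so the normal figures are a fair guide, and they show the same 1-point shortfall.

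*The overall test is a guess from fit.* Correct. The exact matches depend on using n−1 in the noncentrality, and even then the three 18s, the 13 and the 33 are one off. A reader might infer that the table was in fact sized for an overall test. The plan does not say so, and its wording is pairwise.

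*Nothing turns on it.* For accrual this is right, and it sets the severity.

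**Conclusion.** The point holds, as a minor one, in two parts.

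- As extracted, 31 is inconsistent with its two sibling rows, with the table's note and with every method tried. The 33 is a one-patient mismatch. Confidence is high for the text as read, subject to a check of the source.
- If the pairwise tests at 0.025 are two-sided, the 1-point cells deliver 76.6 to 77.8% rather than 80% for A vs B and for A vs C. The 2-point cells are borderline, below 80% by at most about 1.3 percentage points by paired t and above it by the normal approximation. The 3- and 4-point cells meet 80%. These figures take the plan's SD and correlations as given and assume complete data.

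That the table was built on an overall 2-df test is plausible but only inferred, with medium confidence; the pairwise shortfall does not depend on it.

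A reader might also infer that the trial is underpowered because of these errors. The documents do not support that. The largest 2-point requirement is 44 by paired t, below 50, and the 1-point requirements are out of reach of 50 with either set of figures.

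**What to change.** 1. Check 31 and 33 against the source file. If they are there, correct them so that rows with the same difference agree. The sibling rows imply 21 and 32; the final values follow from the method chosen in step 3.
2. State the test behind the table and whether it is one- or two-sided.
3. Recompute the table for the two-sided pairwise comparisons the text names. By paired t, for correlation 0.3 / 0.1 / 0.05: 123 / 157 / 166 for 1 point, 33 / 42 / 44 for 2 points, 16 / 20 / 21 for 3 points and 11 / 13 / 13 for 4 points.
4. Only if the study statistician confirms that the table was sized for an overall test of the three means may it be kept, with the cells in step 1 corrected. A sentence should then say so and give the two-sided pairwise power (paired t) at the printed n: about 77% for 1 point, 79% for 2 points, 83 to 86% for 3 points and 85 to 92% for 4 points.

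The cost is one replacement table, or one or two corrected cells and a sentence. Under step 3 the 1-point cells rise by 9 / 12 / 13, the 2-point cells printed as 32 / 40 / 42 rise by 1 / 2 / 2, and the 3- and 4-point cells fall by one or two (the 31 aside). The accrual target of 50 does not change.
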